**2b: Patient's bedside CRF**

**African Critical Illness Outcomes Study (ACIOS) – Patient CRF**

**Clinical assessment**

Date of assessment:

Vital signs done by the investigating team:  Y  N If no, specify  Vital signs from patient records  Not done

Position of patient:

Lying flat on back(<30°)  Lying on side  Head-up(30°-60°)  Sitting(>60°)  Head-down  Other

Airway patency:  Normal  Partial obstruction  Complete obstruction

Conscious level (AVPU):  Alert  Responds to Voice  Responds to Pain  Unresponsive

Heart rate  /min Oxygen saturation  % Respiratory rate  /min

Systolic blood pressure  /mmHg Diastolic blood pressure  /mmHg

Currently receiving IV fluids  Y  N Receiving oxygen (now)  Y  N

Receiving vasopressor/inotrope (now)  Y  N Airway action (now)  Y  N

Circle the worst pain you had in the last 24 hours: 0 (no pain) 1 2 3 4 5 6 7 8 9 10 (worst pain you can imagine)

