Primary outcomes	
 1. To determine patients’ self-reported severity of pain in the preceding 24 hours on a scale of 0 – 10. 2. To determine the association between severity of pain and critical illness in adult patients admitted to hospitals across Africa. 3. To determine the association between severity of pain and mortality in adult patients admitted to hospitals across Africa.
Data collection duration	One day in each hospital in September-December 2023 plus 7 days follow-up in each hospital
Proposed start date	7 th September 2023
Proposed end date	27 th December 2023

Introduction

Pain is poorly managed in hospitalised patients (Wu and Raja 2011). Uncontrolled pain in hospitalised patients is strongly associated with both short- and long-term complications. Patients are more likely to develop secondary complications such as sepsis, bleeding, and infarctions if their pain is not adequately managed (Brennan, Carr et al. 2007, van Boekel, Warlé et al. 2019). Further, pain of >7 on a visual analogue scale is strongly associated with an increased risk of persistent pain (Sinatra 2010). In high-income countries, up to 86% of hospitalised patients report having poorly managed pain (Wu and Raja 2011, Gan 2017). However, there is a paucity of the literature on the severity of acute pain in hospitalised patients in Africa. Therefore, this sub-study aims to determine the severity of self-reported pain in hospitalised patients across Africa; and the relationship between severity of pain and (1) critical illness and (2) mortality. This study falls under the ACIOS – African Critical Illness Outcome Study – parent study.

2. Statistical Analysis Plan

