Statistical analysis plan for Objective 2 “*association between severity of pain and critical illness*”

Data on 'critical illness' will be extrapolated from the parent study ACIOS.

We will conduct univariate and multivariate logistic regression models to determine the association between severity of pain (continuous variable) and critical illness (binary variable). Severity of pain will be the independent variable and critical illness will be the dependent variable. The independent patient associated with critical illness identified in the primary paper will be included in the multivariate model. We will follow best practice by using both visual data analysis and formal modelling to investigate this relationship. The specifics of the models will be determined by the data features to achieve the best fitting model that is interpretable.

We will use a three-level generalized mixed model, with patients being at the first level, hospital at the second and country at the third level, to account for the expected correlation in outcomes within hospitals and countries.

3.7 Statistical analysis plan for Objective 3 “association between severity of pain and mortality”

The defined time for the outcomes is from the point of inclusion of the patient into the study to hospital discharge or death, censored at 7 days. Patients discharged alive are not followed up at home. Patients still in hospital receiving therapy at 7 days will be regarded as “alive” and included in the study.

We will conduct univariate and multivariable logistic regression models to determine the association between severity of pain (continuous variable) and mortality (binary variable). Severity of pain will be the independent variable and mortality will be the dependent variable. Additional patient factors identified in the primary paper to be independently associated with mortality will be included in the multivariate model. We will follow best practice by using both visual data analysis and formal modelling to investigate this relationship. The specifics of the models will be determined by the data features to achieve the best fitting model that is interpretable.

We will use a three-level generalized mixed model, with patients being at the first level, hospital at the second and country at the third level, to account for the expected correlation in outcomes within hospitals and countries.

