A Kaplan-Meier graph will be constructed of the in-hospital mortality from Day 0 to Day 7 for patients with severe (>7 on VAS) pain and patients *without* severe pain (<7 on VAS). Time will be counted from recruitment to the study until discharge, death or censored. The graph will visualise how mortality risk changes over time. A log-rank test for equality of the survival functions will be performed if the assumptions necessary for using the test hold.(Hosmer, Lemeshow et al. 2008)

Missing data: data from patients lost to follow up (missing outcome data) will be included in the statistical analysis without imputation and reported descriptively. Data from these patients will not be included in the mortality analysis (i.e. objective 3), but will be included in other analyses (i.e. objectives 1 and 2).

References

Brennan, F., D. B. Carr and M. Cousins (2007). "Pain Management: A Fundamental Human Right." *Anesthesia & Analgesia* **105**(1): 205-221.

Gan, T. J. (2017). "Poorly controlled postoperative pain: prevalence, consequences, and prevention." *Journal of Pain Research* **10**: 2287-2298.

Hosmer, D. W., S. Lemeshow and S. May (2008). *Applied Survival Analysis: Regression Modeling of Time-to-Event Data*, Wiley.

RStudio Team (2019). *RStudio: Integrated Development Environment for R*. <http://www.rstudio.com/>.

Sinatra, R. (2010). "Causes and Consequences of Inadequate Management of Acute Pain." *Pain Medicine* **11**(12): 1859-1871.

van Boekel, R. L. M., M. C. Warlé, R. G. C. Nielsen, K. C. P. Vissers, R. van der Sande, E. M. Bronkhorst, J. G. C. Lerou and M. A. H. Steegers (2019). "Relationship Between Postoperative Pain and Overall 30-Day Complications in a Broad Surgical Population: An Observational Study." *Annals of Surgery* **269**(5): 856-865.

Wu, C. L. and S. N. Raja (2011). "Treatment of acute postoperative pain." *The Lancet* **377**(9784): 2215-2225.

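### Objective 3's only time-to-death test splits the 0-10 pain score into >7 and <7; this supporting analysis should be a model on the full score, with the main result named

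*SAP*

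**What the plan says.** The patient case record form (Protocol, Appendix 2b) records pain as one of eleven ordered scores: "Circle the worst pain you had in the last 24 hours: 0 (no pain) 1 2 3 4 5 6 7 8 9 10".

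SAP section 3.7 (Objective 3) keeps that scale for its main analysis: "We will conduct univariate and multivariable logistic regression models to determine the association between severity of pain (continuous variable) and mortality (binary variable". Patient factors found in the primary paper are added, and correlation within hospitals and countries is handled as follows: "We will use a three-level generalized mixed model, with patients being at the first level, hospital at the second and country at the third level".

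The same section then plans a Kaplan-Meier graph over Days 0 to 7. Its upper group is described by "patients with severe (>7 on VAS) pain and patients" and its lower group, those without, by "severe pain (<7 on VAS". The log-rank sentence follows: "A log-rank test for equality of the survival functions will be performed if the assumptions necessary for using the test hold". No Cox or other time-to-event regression is specified, although SAP section 3.1 lists a hazard ratio among the measures that may be reported.

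The only support for the cut is in the SAP Introduction: "pain of >7 on a visual analogue scale is strongly associated with an increased risk of persistent pain". That concerns persistent pain, not death.

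**The concern.** A graph needs groups, but a test does not. The log-rank test treats a score of 0 like a score of 6, and 8 like 10. If mortality changes gradually with pain, which is how the SAP's own model treats it, most of that gradient is thrown away. As written, a score of exactly 7 falls in neither group, so those patients drop out of the comparison. The log-rank sentence also makes no provision for the hospital and country correlation that the same section expects.

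The association of pain with mortality is one of the three listed primary outcomes. It would be tested twice on different scales, with a two-sided 0.05 level and no statement of which result prevails. The two can disagree, and the choice of emphasis would then be made after seeing the data, which the SAP says it wants to avoid.

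**Working it through.** **Inputs from the documents.** Score 0-10 in whole points; groups >7 and <7; two-sided 5% level; follow-up censored at 7 days. The plan states no power, sample size, number of deaths, effect size or pain distribution, so there is no planned figure to reproduce. Everything below that depends on these is an assumption. Clustering is ignored.

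**Formula.** If the log-hazard is linear in the score, the efficiency of the two-group test relative to a trend test on the full score is

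eff = f × p(1 − p) × d² / Var,

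where f is the share of patients kept, p the share of those in the upper group, d the difference in group mean scores, and Var the variance of the score. If the full-scale test has 80% power, the two-group test has power Φ(√eff × (1.96 + 0.84) − 1.96).

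**Worked case, uniform scores.** Var = (11² − 1)/12 = 10.

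- As written: f = 10/11 = 0.909, p = 3/10, means 9 and 3, so d = 6. eff = 0.909 × 0.21 × 36/10 = 0.69. Power = Φ(0.829 × 2.80 − 1.96) = Φ(0.36) = 64%.
- With 7 in the lower group: p = 3/11, p(1 − p) = 0.198, d = 9 − 3.5 = 5.5. eff = 0.198 × 30.25/10 = 0.60. Power = 58%.
- With 7 in the upper group: p = 4/11, p(1 − p) = 0.231, d = 8.5 − 3 = 5.5. eff = 0.70. Power = 65%.

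**Six assumed distributions, full-scale power 80%.**

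| Score distribution | eff as written | Power as written | Loss (points) | Power, 7 in lower group | Power, 7 in upper group |
|---|---|---|---|---|---|
| Uniform | 0.69 | 64% | 16 | 58% | 65% |
| 30% zeros plus uniform | 0.65 | 62% | 18 | 57% | 65% |
| Bell-shaped, mean 5 | 0.51 | 51% | 29 | 45% | 57% |
| Skewed low | 0.42 | 44% | 36 | 42% | 53% |
| 25% zeros plus hump at 5 | 0.35 | 38% | 42 | 34% | 48% |
| Skewed high | 0.76 | 68% | 12 | 60% | 64% |

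The loss is 12 to 42 points as written, and 12 to 46 over all three readings of where 7 belongs. These ranges describe the cases tried; they are not bounds.

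**Dependence on deaths.** Take uniform scores and an assumed hazard ratio of 1.05 per point (log 0.0488). With E deaths, full-scale power is Φ(√(10E) × 0.0488 − 1.96). Two-group power is Φ(√(0.909E × 0.21) × 6 × 0.0488 − 1.96). For E = 200 these are Φ(2.18 − 1.96) = 59% and Φ(1.81 − 1.96) = 44%.

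| Deaths | Full score | >7 v <7 |
|---|---|---|
| 200 | 59% | 44% |
| 400 | 87% | 73% |
| 800 | 99% | 95% |
| 1500 | 100% | 100% |

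**Disagreement.** In 7-day simulations with about 110 to 575 deaths and full-scale power of 86 to 96%, the two-group test lost 7 to 12 points. The two tests disagreed on significance in 8 to 16% of runs. With about 540 to 600 deaths and a log-hazard of 0.10 per point, both had power 100% and never disagreed.

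**If risk is flat and then steps up above 7.** With 7 in the lower group, eff is the squared correlation between score and group, so it applies equally in the other direction. When the two-group test has 80% power, the linear trend test then has the power in the table's fifth column, 34 to 60%. The order is reversed.

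**The case against.** The strongest reply is that the mortality question is already tested on the full scale. The logistic mixed model takes pain as continuous; the log-rank test is conditional on its assumptions and accompanies a graph meant to visualise risk over time. Testing two plotted curves is ordinary practice, and no text makes that test decisive. This stands, and it limits the point to a supporting analysis.

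Second, no single loss can be derived from the documents. Recruitment is open-ended, so 80% is an arbitrary anchor, and with many deaths the loss is negligible. This also stands. So does the dependence on a linear effect: the SAP posits no mortality threshold at 7, but it leaves the final model form to the data and does not rule one out.

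Third, swapping the log-rank test for a Cox model still leaves two tests, and an unadjusted Cox model would sit awkwardly beside an adjusted logistic one. That is a fair demand on the fix, which must carry the same patient factors and say which result leads.

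What remains is that the plan's one time-to-death test is on a coarser scale than the data and than its own main model, with no stated reason tied to mortality and no rule for disagreement.

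**Conclusion.** The point holds as a minor improvement to a supporting test. Under a log-linear effect and 80% full-scale power, the test as written loses roughly 12 to 42 points (12 to 46 over all readings of where 7 belongs). The loss nears zero with many deaths and changes sign if risk rises only above 7. The pain distributions, hazard ratios and death counts are all assumed.

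A reader might infer that Objective 3 as a whole is underpowered, that a fixed loss applies whatever the data, or that a non-significant log-rank result would be reported as no association. The documents support none of these. The main model keeps the full score, no figures are given from which a loss could be fixed, and SAP section 3.1 calls for estimates with 95% confidence intervals, so the continuous-score result would appear alongside.

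**What to change.** In SAP section 3.7, keep the two-group Kaplan-Meier curve for display, stating where a score of 7 is plotted. Drop any log-rank p-value or label it descriptive. Replace the log-rank sentence with:

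'The time-to-death association will be estimated with a Cox (cause-specific hazard) model with the 0-10 pain score as a continuous term, the same patient factors as the multivariable logistic model, and hospital and country as random effects. The continuous-score logistic mixed model is the primary result for Objective 3; the Cox model is supporting.'

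This also provides the hazard ratio that section 3.1 lists. The cost is two sentences and one extra model in R, which the SAP already names. No new data are needed: the case record form holds the score, the assessment date and the date of discharge or death. The small downside is that the p-value no longer refers to the two plotted curves.
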